6.3.6 UNSCHEDULED VISIT

All unscheduled visits will be recorded

6.3.7 SCHEDULE OF EVENTS TABLE

Procedures	Screening	Enrollment/Baseline Visit 1, Day 0	Day 1	, Day 2-	, Day 3-	, Day 4-	, Day 5-	, Day 6-	, Day 7-
Informed consent & Randomization		X							
Demographics & Medical History		X							
Aesthetic Treatment		X							
Subject Questionnaire	X	X	X	X	X	+/-X	+/-X	+/-X	+/-X
Exam for Adverse Effects		X	x	x	x	+/- x	+/- x	+/- x	+/- x
Exam by blinded Evaluator		X							
Intervention with Face Mask		X	x	x	x	+/- x	+/- x	+/- x	+/- x
Photos		X	x	x	x	+/-x	+/-x	+/-x	+/-x

6.3 Photography

Photographs will be taken 30 minutes after application of the intense hydration mask. Photographs may also be taken to document AEs at the treating investigator's discretion. Site personnel will be thoroughly trained in the photographic equipment and techniques before study start. A Photography Standard Operating Procedure will be provided in a separate user guide.

6.4 Subject Questionnaires

Subjects will be asked about their satisfaction with the facemask using a subject Satisfaction questionnaire.

6.3 PROHIBITED MEDICATIONS, TREATMENTS, AND PROCEDURES

Treatment with any prescription oral anti-coagulants, corticosteroids, or immune-modulating medications are prohibited. In the event a subject takes these medications or has treatments or procedures before the laser treatment, the primary investigator will make the final decision regarding early termination from the clinical trial.

6.4 PROPHYLACTIC MEDICATIONS, TREATMENTS, AND PROCEDURES

If the patient has a history of herpes simplex on the face, they will be allowed to use prophylactic anti-viral medications.

6.5 RESCUE MEDICATIONS, TREATMENTS, AND PROCEDURES

If patients develop an infection during the trial, they will be prescribed the appropriate anti-viral or anti-bacterial medication but will continue in the study.

7 ASSESSMENT OF SAFETY

Safety evaluations for this study include an interview of the subjects to obtain information about any medical occurrence that meets the definition of an AE. Each subject should be questioned about AEs at the study visit following the screening visit. The question should be asked: "Since your last clinical visit have you had any health problems?" Information on AEs can also be obtained from signs and symptoms detected during the examination by the evaluator, which should include visual inspection of the treatment area.

AEs must be documented in the source document without regard for cause or relation to investigational product. If in the process of the interview, additional information regarding medical history or preplanned medical or surgical procedures is revealed, it must be documented in the source documents.

It is the responsibility of the Investigator to determine severity of the AE and relatedness of the event to the study product.

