3.2.2 SECONDARY ENDPOINTS

- The difference in the number of adverse events between the two sides of the face
- The difference in pain scores on each side of their face as rated by subjects
- The difference in patient satisfaction scores when rating the procedure on the left and right side of their face
- The difference in erythema on the left and right side of subject's faces as graded by blinded evaluators doing live assessments 30 minutes after the procedure
- The difference in healing time in daily photographs as rated by blinded evaluators

These endpoints will show if the Velez Intense Hydration face mask decreases skin temperature after a cosmetic procedure, if subjects are happy with the use of the mask, and if they provide significant reduction in pain, erythema, and healing time.

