6.2 STUDY SCHEDULE

6.2.1 SCREENING

Screening Visit (Day -60 to 0)

- Send out and review subject questionnaires to determine eligibility based on inclusion/exclusion criteria.
- Schedule study visits for participants who are eligible and available for the duration of the study.
- Provide participants with specific instructions needed to prepare for first study visit and all subsequent visits.

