6.2.2 ENROLLMENT/BASELINE

Enrollment/Baseline Visit (Visit 1, Day 0)

- Review in depth the study design with subjects and obtain informed consent of potential participants verified by signature
- Perform examination and verbally review subject's medications and medical history to determine eligibility based on inclusion/exclusion criteria.
- Verify all inclusion/exclusion criteria.
- Obtain demographic information
- Randomization
- Perform either a Sciton Moxi, Sciton Erbium, or Secret RF treatments to subject's face, and then apply a half mask on one side of the face according to randomized groups.
- Record adverse events as reported by participant or observed by investigator or blind evaluator.
- Perform protocol adherence check by study coordinator
- Collect post-procedure subject questionnaires
- Take post-procedure photos

- After photographs and blind evaluation both side of the face will be treated with the normal post-procedure care such as Vaseline for laser resurfacing and a Hydrating serum for Moxi and Microneedling. Additional masks will be given to patients to wear for 2 hours at home each day until deemed healed by the primary investigator.

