7.5 RECORDING INSTRUCTIONS

Investigators, or other study site personnel, shall record all AEs including:

- a) Event term (recorded in standard medical terminology and avoiding abbreviations)
- b) Affected area
- c) Start date (first day with symptoms)
- d) Stop date (last day with symptoms)
- e) Intensity (mild, moderate, or severe)
- f) Seriousness (serious or not serious)
- g) Causal relationship to study product or study product injection procedure (yes or no)
- h) Action taken (none, medication treatment, non-pharmacological treatment, or other procedures/tests, subject withdrawn)
- i) Outcome of the AE (ongoing, recovered, recovered with sequelae, death, chronic/ stable, not recovered at the end of the study)

All AEs, non-serious as well as serious, are to be reported as an AE. The PI will record all reportable events with start dates occurring any time after informed consent is obtained until 7 (for non---serious AEs) or 14 days (for SAEs) after the last study intervention. At each study visit, the investigator will inquire about the occurrence of AE/SAEs since the last visit. Events will be followed for outcome information until resolution or stabilization.

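### Section 7 ties the adverse-event interview to the Day 0 visit, against the every-visit rule in 7.5 and 7.6.1, and neither its question nor the follow-up wording fits the between-side AE endpoint

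*Combined protocol and SAP*

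**What the plan says.** Section 7 (Assessment of Safety) sets the timing of the interview: "Each subject should be questioned about AEs at the study visit following the screening visit". It supplies one question to put to the subject: "Since your last clinical visit have you had any health problems". It adds that AEs may also come from the evaluator's examination, including inspection of the treated area.

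Section 7.5 sets a different timing, and 7.6.1 repeats it word for word: "At each study visit, the investigator will inquire about the occurrence of AE/SAEs since the last visit". Neither section gives a wording for the question.

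The AE endpoint is listed first among the secondary endpoints, in the Protocol Summary and in 3.2.2: "The difference in the number of adverse events between the two sides of the face". Section 6.3.3 has follow-up visits record participant-reported AEs on the side assigned the mask and does not mention the other side.

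**The concern.** Two instructions on when to ask about AEs cannot both be followed as written. The one that carries the scripted question attaches it to the visit where the look-back is least informative. Home wear of at least 2 hours a day comes after that visit. The mask risks listed in 2.3.1 include itching and pain, which a photograph may not show. With two study centers, staff could elicit AEs differently depending on which section they work from.

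The second issue is side. A difference between sides can be interpreted only if both sides are asked about and recorded in the same way. A general-health question prompts for neither side, and the follow-up wording prompts for only one. With 15 subjects, a few events elicited unevenly could change the between-side count.

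**Working it through.** The plan states no figure on this point. The check sets the sections side by side and counts visits.

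1. **Which visit follows screening.** Section 6.2.1 gives "Screening Visit (Day -60 to 0" as the window, and the next visit, in 6.2.2, is "Enrollment/Baseline Visit (Visit 1, Day 0". Section 7 therefore names Day 0.

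2. **How many visits each rule covers.** Follow-up lasts 3 to 7 days (Schematic of Study Design; 6.3.7).
   - Section 7, read literally: 1 visit.
   - Sections 7.5 and 7.6.1: from 1 + 3 = 4 to 1 + 7 = 8 visits.
   - The sections disagree on 3 to 7 visits per subject, which are all the follow-up visits.

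3. **What the question covers if asked at Day 0.** The previous study contact is screening, described in 6.2.1 as: "Send out and review subject questionnaires to determine eligibility based on inclusion/exclusion criteria". No examination is listed there, so the last clinical visit in the ordinary sense may be earlier still. Counted from screening, the look-back is 0 to 60 days.

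4. **How much of that look-back counts.** Section 7.5 starts AE recording at informed consent, which 6.2.2 and 6.3.7 place on Day 0. Section 7.6.1 treats conditions present at screening as baseline. Of a look-back of up to 60 days, only the part of Day 0 after consent can yield a recordable AE.

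5. **How much of it involves the mask.** In 6.2.2, staff perform the procedure and then "apply a half mask on one side of the face according to randomized groups"; AE recording is listed after that step. Section 5.1.7 gives 30 minutes of wear in the office. A question put at the end of Visit 1 could therefore cover that first half hour. One put earlier in the visit covers none of it.

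6. **Whether side is elicited.** The Section 7 question names no side, and 6.3.3 names the mask side only. Section 7.5 requires the affected area to be recorded, but that applies to an event once it has come to light and does not prompt for one. The endpoint is by side of the face. Only the temperature endpoint is measured at the cheek (Protocol Summary; 3.2.1, Primary Endpoint).

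**The case against.** The strongest reply is that Section 7 is loosely worded and the rest of the plan is clear. The sentence does not say that AEs are asked about only then, and it may have been meant to cover the visits after screening. The look-back in the question matches the one in 7.5 and 7.6.1, so the question works unchanged at any follow-up visit. AE capture after Day 0 is required in several places:

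- the inquiry at each visit in 7.5 and 7.6.1;
- the recording step in 6.3.3;
- the exam row in 6.3.7;
- the daily safety assessment in the Schematic;
- review of questionnaires as an AE source in 7.6.1;
- pain as a safety endpoint at follow-up in 7.8.

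All of this stands, and it rules out two readings that a reader might otherwise draw. The first is that 3/4 = 75% to 7/8 = 87.5% of visits have no solicited AE inquiry, leaving Days 1 to 7 to volunteered complaints. That is the arithmetic of one sentence read in isolation. The plan as a whole requires inquiry at all of those visits, so the percentages measure no loss of data. The second is that a general question misses one-sided reactions, or that control-side events go uncollected. The documents do not show either: the question may miss such reactions, and 7.5 still calls for all AEs to be recorded, with their affected area.

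The reply leaves two things unanswered. The conflicting sentence remains in the section that holds the only scripted question. None of the listed provisions asks the subject about each side in the same terms.

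**Conclusion.** The point holds as an internal inconsistency with a gap in how side is elicited. Section 7 names one visit where 7.5 and 7.6.1 require 4 to 8. At the visit it names, the look-back lies mostly before consent and before the mask, apart from a possible first 30 minutes of wear. The effect on the AE count cannot be sized from the documents, and the primary temperature endpoint is unaffected.

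The more consequential part is that the general question and the mask-side wording in 6.3.3 do not support a comparison between sides. This rests on two assumptions: that Section 7 is read as written, and that staff treat 6.3.3 as their instruction for what to record at follow-up. If both sites already ask about both sides at every visit, the change only makes the text match practice.

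**What to change.** - **Section 7:** replace the timing sentence with one stating that AEs are asked about after the procedure and mask period on Day 0 and at every follow-up visit through the last, as in 7.5, 7.6.1 and the schedule in 6.3.7. Have the Day 0 question refer to the time since the procedure; the existing look-back can stay for follow-up visits.
- **Question:** after the general question, ask the same thing separately about the left and the right side of the face, not only the cheeks. Using left and right rather than masked and unmasked keeps the assignment out of the wording.
- **Section 6.3.3:** amend it so that AEs are recorded for both sides.

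The cost is protocol wording and one extra question per side at visits already scheduled. Section 7.5 gives the inquiry to the investigator, so the rule in 8.7.1 against discussion between evaluator and subject is not disturbed. The downside is that direct questioning will raise the number of mild AEs reported. Subjects know which side is masked (6.1.1), so the increase may not be equal between sides, and the between-side comparison should be read with that in mind.

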7.1 ADVERSE EVENTS

7.1.1 DEFINITION OF SERIOUS ADVERSE EVENTS (SAE)

Adverse event means any untoward medical occurrence associated with the use of an intervention in humans, whether considered intervention-related (21 CFR 312.32)

Serious adverse event or serious suspected adverse reaction.

An adverse event or suspected adverse reaction is considered "serious" if, in the view of either the investigator or sponsor, it results in any of the following outcomes: death, a life-threatening adverse event, in-patient hospitalization or prolongation of existing hospitalization, a persistent or significant incapacity or substantial disruption of the ability to conduct normal life functions, or a congenital anomaly/birth defect. Important medical events that may not result in death, be life-threatening, or require hospitalization may be considered serious when, based upon appropriate medical judgment, they may jeopardize the patient or subject and may require medical or surgical intervention to prevent one of the outcomes listed in this definition.

7.3.2 DEFINITION OF UNANTICIPATED PROBLEMS (UP)

Unanticipated problems involving risks to participants or others to include, in general, any incident, experience, or outcome that meets all the following criteria:

- Unexpected in terms of nature, severity, or frequency given (a) the research procedures that are described in the protocol-related documents, such as the IRB-approved research protocol and informed consent document; and (b) the characteristics of the participant population being studied;

- Related or possibly related to participation in the research (“possibly related” means there is a reasonable possibility that the incident, experience, or outcome may have been caused by the procedures involved in the research); and
- Suggests that the research places participants or others at a greater risk of harm (including physical, psychological, economic, or social harm) than was previously known or recognized.

With these events the following will occur:

- *Modification of inclusion or exclusion criteria to mitigate the newly identified risks*
- *Implementation of additional safety monitoring procedures*
- *Suspension of enrollment of new participants or halting of study procedures for enrolled participants*
- *Modification of informed consent documents to include a description of newly recognized risks*
- *Provision of additional information about newly recognized risks to previously enrolled participants.*

7.4 CLASSIFICATION OF AN ADVERSE EVENT

7.4.1 SEVERITY OF EVENT

- **Mild** – Events require minimal or no treatment and do not interfere with the participant’s daily activities.
- **Moderate** – Events result in a low level of inconvenience or concern with the therapeutic measures. Moderate events may cause some interference with functioning.
- **Severe** – Events interrupt a participant’s usual daily activity and may require systemic drug therapy or other treatment. Severe events are usually potentially life-threatening or incapacitating.

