2 INTRODUCTION: BACKGROUND INFORMATION AND SCIENTIFIC RATIONALE

2.1 BACKGROUND INFORMATION

Aesthetic procedures are gaining popularity; however patients are always interested in less downtime and pain. With non-ablative laser and microneedling with radiofrequency, patients experience less, however even the few hours of pain and erythema may be decreased by post-procedure products making these treatments even easier to tolerate with less downtime. Additionally, ablative laser resurfacing still provides the best cosmetic results, however the pain and downtime often limits who is willing to do the procedure. Products that can decrease pain and erythema as well as quicken the healing phase are needed to enable more patients to undergo these cosmetic treatments.

While topical ice or a fan are sometimes used to decrease the pain and heat associated with procedures, these require the patient to remain in the office often in an exam room to either hold the ice or to utilize a specialized fan (Zimmer Chiller). This elongates the procedure time for both the patient and the treating provider. The advantage of the face mask is that it is self-adhering to the face and requires no additional time in the office or specialized planning since the masks do not need to be kept in a fridge. Velez intense hydration masks are made of bio cellulose material obtained from vegetable raw materials and are self-adhering providing mobility and immediate comfort.

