3 STUDY DESIGN, OBJECTIVES, AND ENDPOINTS

3.1 DESCRIPTION OF THE STUDY DESIGN

- A Prospective, Multi-Arm, Split-Face, Randomized Clinical Trial
- 2 Study Centers
- Study agent: Velez Intense Hydration Mask
- Study Intervention on Day 0
- Live evaluations by Blinded Evaluators on Day 0
- Daily photographic evaluations by Blinded Evaluators

This will be a prospective, multi-arm, evaluator blind, split-face, clinical trial in which subjects will be randomized to 2 groups in 3 separate arms.

1st Arm (n=5) Non-ablative fractionated Thulium laser (Sciton Moxi)

2nd Arm (n=5) Ablative full Erbium:Yag laser (Sciton Contour)

3rd Arm (n=5) Microneedling with RF (Cutera Secret)

In each arm, there will be two groups

1st group: Velez Intense Hydration Facemask on the left side of their face and nothing on the right

2nd group: Velez Intense Hydration Facemask on the right side of their face and nothing on the left side

Both groups will be utilizing the same safety and comfort protocols established by the practice which include the use of topical numbing cream (B.L.T.) before the laser procedure and cleansing with a makeup wipe and alcohol.

After the procedure a blind evaluator will be grading the subjects' erythema, edema, and any side effects. A compliance analysis performed by study coordinator will be done each visit.

Thirty minutes after the laser procedure, digital photography using Canfield's imaging system, and a thermal camera will be done. In addition, a subject questionnaire on satisfaction, erythema, edema and pain levels after the procedure will be completed. Patients will then have the typical post-care treatment on both sides of their face such as Vaseline for laser resurfacing and a hydrating serum for the Moxi and Microneedling. They will apply the mask at home for at least two hours each day and then return to the office daily for questionnaires and photographs until deemed fully healed by the primary investigator.

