8.3 SAFETY ANALYSIS

Safety analysis will be descriptive only.

The number and percentage of subjects reporting each post-treatment symptom will be presented in total and by maximum severity.

A summary of all AEs will be provided, which will include:

- number of subjects with at least one AE and number of events (in total as well as serious AEs)
- number of subjects with at least one related AE and number of events (in total as well as serious AEs)
- number of subjects with at least one mild, moderate, and severe AE and number of events (in total as well as serious AEs)
- number of subjects with at least one unrelated AE and number of events (in total as well as serious AEs)
- number of subjects who did not have an AE

The number of subjects with AEs related to the study product as well as the number of events will be summarized, and action taken for related AEs will also be summarized. Serious AEs will be listed.

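### The AE severity scale has no local criterion and the severity tables have no split by cheek, so they cannot show whether the mask made a cheek better or worse

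*Combined protocol and SAP*

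**What the plan says.** Section 7.4.1 has three grades for every adverse event (AE):

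- Mild: "Events require minimal or no treatment and do not interfere with the participant’s daily activities".
- Moderate: slight inconvenience or worry, with the addition that "Moderate events may cause some interference with functioning".
- Severe: events that break into the participant's "usual daily activity and may require systemic drug therapy or other treatment. Severe events are usually potentially life-threatening or incapacitating".

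Section 7.5 asks for an affected area and an intensity on each AE record. Section 8.3 makes safety descriptive. It states that "The number and percentage of subjects reporting each post-treatment symptom will be presented in total and by maximum severity", and it also lists counts of subjects and events at each grade. No line of that section mentions the side of the face.

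The first secondary endpoint in section 3.2.2 is "The difference in the number of adverse events between the two sides of the face". For Days 1 to 7, section 6.3.3 asks for participant-reported AEs on the masked side and does not mention the other side. The schedule in section 6.3.7 has an AE examination on Day 0 and at every follow-up visit, without restriction to a side. It has the blinded-evaluator examination on Day 0 only. For that day section 3.1 says: "After the procedure a blind evaluator will be grading the subjects' erythema, edema, and any side effects".

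**The concern.** The trial compares two cheeks of one person, and the safety of the mask is its first secondary objective. Section 2.3.1 lists six possible reactions to the mask. Five of them (swelling, itching, pain, dermatitis, erythema) are also listed for the procedures, which are done on both sides. A reaction of these kinds can therefore appear on both cheeks. Where it does, the count of AEs ties and only intensity can separate the masked cheek from the unmasked one.

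A scale built on the participant's daily life is poorly suited to that comparison, and a table that pools the cheeks cannot make it at all. At stake is whether the report can say anything about local worsening or relief under the mask from its AE severity data. Severity also enters the judgement of expectedness in section 7.4.3, so an unclear grade boundary has some effect beyond the tables.

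**Working it through.** The plan gives no figure for AE severity, so there is none to reproduce. The check sets the sections side by side and works through what the planned tables would print.

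**Step 1: the grading criteria (section 7.4.1).** Mild turns on treatment need and interference with daily activities. Moderate turns on inconvenience and interference with functioning. The first Severe sentence turns on "usual daily activity and may require systemic drug therapy or other treatment". None of the three uses the extent or intensity of a local sign. Interference with daily life has one value per person at a given time. Treatment need can differ by cheek, but it is the only criterion that clearly can.

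**Step 2: the Moderate/Severe boundary.** The first Severe sentence is met by an interruption of usual activity. The second says such events are usually potentially life-threatening or incapacitating, which is a much higher level. Moderate already admits some interference. An event that interrupts activity for a time but is far from incapacitating fits part of each definition.

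**Step 3: the severity tables (section 8.3).** Inputs: 15 subjects (section 8.1) and, as an assumption for illustration, 5 subjects with one Severe event each.

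| Pattern | Masked cheek | Unmasked cheek | Row printed under 8.3 |
|---|---|---|---|
| A | 5 subjects | 0 subjects | 5/15 = 33.3%, 5 events |
| B | 0 subjects | 5 subjects | 5/15 = 33.3%, 5 events |

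The masked-minus-unmasked difference is 5 − 0 = +5 in A and 0 − 5 = −5 in B, yet the printed rows are identical. This remains so even if every cheek is graded perfectly.

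Maximum severity loses the same information. A subject with Moderate swelling on one cheek and Mild on the other is entered as Moderate, whichever cheek was masked.

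**Step 4: follow-up recording (section 6.3.3, read literally).** If swelling starts on Day 1 on both cheeks, the record shows masked 1, unmasked 0, difference +1; the true difference is 1 − 1 = 0. If it starts on the unmasked cheek only, the record shows 0 − 0 = 0; the true difference is 0 − 1 = −1. Both errors count against the mask. Sections 6.3.7 and 7.5 can be read as asking for all AEs on either side, so the sections disagree.

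**Step 5: what a by-cheek table could show.** With a grade per cheek, each subject is a matched pair. If all m discordant pairs point the same way, the exact two-sided sign-test p-value is 2 × 0.5^m:

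- m = 5 (one whole arm): 2 × 0.03125 = 0.0625.
- m = 6 (pooled): 2 × 0.015625 = 0.031.

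Such a table would be readable as description, with little power within an arm. That fits the descriptive safety plan.

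**The case against.** The strongest reply is that AE records are event-based. Section 7.5 takes an affected area and an intensity for each event, so a reaction on one cheek has its own grade, and two events in one person may be graded differently. This stands. A reader might infer from section 7.4.1 that both cheeks of one person must receive the same grade, but the documents do not say so. What remains is narrower: the location is recorded, but the scale offers little by which to grade two reacting cheeks apart, and section 8.3 does not use the location.

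A reader might also infer that ordinary recovery after ablative resurfacing would be entered as Severe, because section 2.1 says that "the pain and downtime often limits who is willing to do the procedure". The documents do not support this. Moderate already covers some interference, and the second Severe sentence describes something well beyond normal recovery. Section 2.1 neither says that usual activity is interrupted nor calls downtime an AE. The oral drugs for the ablative arm in section 2.3.1 are prophylaxis, not treatment of an event. Only the unclear boundary stands.

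Third, the consequences are limited. Safety is descriptive, the between-side AE endpoint concerns number and not severity, and section 3.2.2 compares pain, erythema at 30 minutes and healing time by side. This also stands in part. Those measures do not cover itching, dermatitis or hypersensitivity, and the blinded erythema grading is on Day 0 only.

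Finally, the counts of product-related AEs in section 8.3 might seem to stand in for side. They are listed separately from the severity counts, and relatedness is a judgement about cause, not a record of which cheek reacted.

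**Conclusion.** The point holds as a gap in the scale, the recording instruction and the tables taken together. The larger cause is the absence of any split by cheek in section 8.3, made worse by the masked-side wording in section 6.3.3. The scale in section 7.4.1 contributes by offering no local criterion. As written, the severity tables cannot inform the first secondary objective in either direction: they would hide benefit as readily as harm.

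The documents give no AE rates, so the number of affected events cannot be estimated. The 5 of 15 rows are an illustration with assumed counts. The sample of 15 and the arm size of 5 are group sizes and should not be read as expected numbers of tied or Severe events. Overlap between the two risk lists shows that two-sided reactions are possible, not how common they will be.

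The conclusion assumes that section 8.3 is programmed as written, without an added side split. The direction of the counting error in Step 4 assumes a literal reading of section 6.3.3. The primary endpoint is not affected. This is a worthwhile, inexpensive correction and not a flaw that endangers the trial.

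**What to change.** - **Section 6.3.3:** record AEs on both cheeks at every visit, so that it agrees with the endpoint in section 3.2.2 and the schedule in section 6.3.7.
- **Sections 7.4.1 and 7.5:** add a side-specific intensity entry for local facial reactions, completed at the AE examination already scheduled at each visit. Keep the daily-activity scale for events not confined to the treated skin, and reword the two Severe sentences so that the boundary with Moderate is clear.
- **Section 8.3:** present AE counts and maximum severity of local reactions for the masked versus the unmasked cheek within subject, descriptively.

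The cost is two severity scales instead of one, an extra field per cheek on the AE form and one paired table. Per-cheek items may also be needed on the follow-up questionnaire. Section 3.1 lists erythema, edema and pain for the 30-minute questionnaire, and section 7.8 confirms pain at follow-up, but daily ratings of erythema and edema for each cheek are not clearly collected now. Because the blinded examination is on Day 0 only, later grades may come from staff who know the side, and the table should say so.
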